#### 6.11.4.2 Proportion of subjects experiencing a confirmed $>30\%$ decrease from baseline in eGFR at each timepoint.

Percent eGFR change for a subject at a given visit will be calculated as:

- $\frac{\text{change from baseline}}{\text{Baseline}} \times 100$

At any two consecutive time points, a subject that achieves a clinically significant  $>30\%$  decrease in eGFR from baseline will be considered a confirmed eGFR drop subject at the earlier timepoint, otherwise they will be considered a non-eGFR drop subject. The proportion of subjects with a confirmed eGFR drop at each visit will be compared using the Chi Square or Fisher exact test if applicable. The proportion of eGFR drop subjects will be summarized at weeks 2, 4, 8, 12, 16, 20, 24, 30, 36, 42, 48 and 52 by treatment group. P-values of the differences at each visit will be reported (Table 14.2.7).

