### **1.2.5 Potential Toxicities**

Voclosporin has been studied in numerous disease states. When examining LN, there were a small proportion of voclosporin treated subjects that experienced an early drop of  $\geq 30\%$  in eGFR, however that proportion then remains stable over time. None of these treatment-emergent adverse events (TEAEs) were classed as serious. The majority of TEAEs of decreased GFR were classed as mild or moderate, and resulted in permanent discontinuation of study drug in 1 (1.1%) placebo subject, 6 (6.7%) voclosporin low-dose subjects and 5 (5.6%) voclosporin high-dose subjects. There were more TEAEs of hypertension seen in the voclosporin-treated patients compared to placebo however, overall mean systolic and diastolic blood pressure (BP) decreased in all groups, without statistically significant differences seen between groups. Overall, only 1 (1.1%) subject, in the voclosporin high-dose group, had a TEAE of hypertension that resulted in permanent discontinuation of study drug.

There was evidence of an increased incidence of TEAEs over placebo and with increased dose of voclosporin in the System Organ Classes of Infections and Infestations, Gastrointestinal Disorders, and Vascular Disorders.

There were more deaths in the voclosporin low-dose arm (10) than in either the voclosporin high-dose (2) or placebo (1) arms, with the majority (11/13) occurring in South-East Asia. All deaths were assessed by the Investigator and Data and Safety Monitoring Board (DSMB) as unrelated to study treatment. A full description of adverse events can be found in the IB.

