#### **7.6.1.1 Decrease in eGFR $>30\%$ and eGFR $<60$ mL/min/1.73 m^2**

During the treatment period, any subject experiencing a  $>30\%$  decrease in eGFR from baseline to  $<60$  mL/min/1.73 m^2, will have study treatment interrupted until a repeat test can be performed (unscheduled visit to be completed). If the decrease is confirmed and not due to potential contributing factors (e.g., high baseline eGFR, the addition or modification of non-steroidal anti-inflammatory drugs (NSAIDs), angiotensin converting enzyme (ACE) inhibitors, angiotensin II receptor blockers (ARBs), a concurrent state of dehydration, overdosing with study treatment, lupus renal flare, etc.), the case should be discussed with the

Medical Monitor, the study treatment should be withheld, and eGFR retested within 48 hours. If the eGFR decrease is not confirmed, the study treatment can be restarted at 2 capsules BID and increased as tolerated with discussion with the Medical Monitor.

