### **6.2.11 Unscheduled Visits**

All visits whether scheduled or unscheduled will be mapped to the closest scheduled protocol visit according to the protocol schedule of assessments. However, visits, when sorted by visit number and visit date, must remain in chronological order. In summary tables by visit, a subject's latest observation per visit will be tabulated. For assessments of continuous periods of remission, all available observations will be used.

All assessments will be listed in the relevant appendices to the CSR.

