### 6.11.1 Primary Endpoint

The primary endpoint is the number of subjects showing renal response at 52 weeks. Renal response at Week 52 will be adjudicated by the CEC based on the following parameters:

- UPCR of  $\leq 0.5$  mg/mg, and
- eGFR  $\geq 60$  mL/min/1.73 m^2 or no confirmed decrease from baseline in eGFR of  $>20\%$ , and
- Received no rescue medication for LN, and
- Did not receive more than 10 mg prednisone for  $\geq 3$  consecutive days or for  $\geq 7$  days in total during Weeks 44 through 52, just prior to the renal response assessment

The CEC will be blind to treatment group and completely independent of Aurinia. They will also take into consideration the following:

- Subjects who withdraw from the study prior to the Week 52 assessment and thus provide insufficient Week 52 data will be defined as non-responders
- Medication listings will be reviewed by the CEC as part of the adjudication process. The CEC will have complete autonomy to adjudicate any treatment as rescue medication. However, as any dose of MMF is permitted within this protocol there is no MMF dose level that necessarily classifies it as being rescue medication. As part of this review the CEC will also adjudicate on steroid drug use beyond the protocolled taper.

- eGFR values eliminating a subject from complete remission should be accompanied by a treatment or disease-related TEAE that impacts eGFR. To this end, eGFR measures which would ordinarily result in a subject not being in remission will only be used if the first eGFR assessment occurs on a date where there is also a treatment or disease-related, eGFR associated TEAE. The following is a list of MedDRA preferred terms that are associated with eGFR decreases:
  - BLOOD CREATININE INCREASED
  - CREATININE RENAL CLEARANCE DECREASED
  - GLOMERULAR FILTRATION RATE DECREASED
  - SERUM CREATININE INCREASED
  - RENAL IMPAIRMENT
  - RENAL FAILURE
  - RENAL FAILURE ACUTE
- Confirmation of eGFR decreases from baseline require that two consecutive measures at least 3 days apart exhibit the decrease.

The null hypothesis  $H_0$  will be rejected in favor of  $H_1$  if there is evidence at the 5% significance level using a 2-sided test.

$H_0$ : There is no statistically significant difference in renal response between voclosporin and placebo at Week 52

$H_1$ : There is a statistically significant difference in renal response between voclosporin and placebo at Week 52.

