- Did not receive more than 10 mg prednisone equivalent for  $\geq 3$  consecutive days or for  $\geq 7$  days in total during Weeks 44 through 52, just prior to the renal response assessment
- “eGFR success” will also be summarized by individual components:
  - eGFR  $\geq 60$
  - eGFR  $< 60$  with no confirmed decrease  $> 20\%$
  - eGFR  $< 60$  with confirmed decrease  $> 20\%$  but with no disease-related or treatment-related eGFR associated AE present at time of assessment.

Confirmed decrease  $> 20\%$  in eGFR is two consecutive measurements, three or more days apart by the visit where response is defined.

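### SAP 6.11.4.2 confirms a >30% eGFR fall by a slower rule than SAP 6.11.1, so falls confirmed on retest but recovered by the next visit are probably not counted

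*SAP*

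**What the plan says.** The SAP uses the word confirmed for eGFR decreases under two different rules.

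- **Renal response.** SAP 6.11.1 states: "Confirmation of eGFR decreases from baseline require that two consecutive measures at least 3 days apart exhibit the decrease". SAP 6.11.2.3 repeats this for the >20% component: "two consecutive measurements, three or more days apart by the visit where response is defined".
- **The >30% endpoint.** SAP 6.11.4.2 reads "At any two consecutive time points, a subject that achieves a clinically significant" fall of more than 30%, and such a subject "will be considered a confirmed eGFR drop subject at the earlier timepoint". Percent change is calculated at a visit. The arms are compared visit by visit at 12 listed weeks, from Week 2 to Week 52 (Table 14.2.7). The section does not refer to 6.11.1 and defines neither the qualifier nor what counts as a time point.
- **Visit mapping.** SAP 6.2.11: "All visits whether scheduled or unscheduled will be mapped to the closest scheduled protocol visit". Where several values share a visit label, by-visit summaries use only the most recent. The one exception that uses every observation is for continuous periods of remission.
- **What happens on site.** Protocol 9.2.5 requests an unscheduled visit for any eGFR decrease above 30%. Under Protocol 7.6.1.1, where eGFR has also fallen below 60, the subject "will have study treatment interrupted until a repeat test can be performed (unscheduled visit to be completed").
- **Status.** SAP 3.2.2 lists the endpoint among the other secondary endpoints, and SAP 9 takes it out of the hierarchical testing.

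**The concern.** A reader of the results would expect confirmed to mean the same thing throughout one SAP. It does not, and the difference works in one direction. The trial's own procedure responds to a large fall with a prompt retest, and with interruption of study treatment where eGFR is also below 60. Protocol 2.1 describes the renal risk as dose-related, reversible and manageable by reducing or interrupting the dose. The falls most likely to be confirmed on retest and gone by the next visit are therefore acute, reversible ones, and these are the ones that a two-visit rule drops. For a calcineurin inhibitor they plausibly occur more often on active drug.

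The qualifier adds a second uncertainty. It appears in neither SAP 3.2.2 nor the protocol's endpoint lists (3.3.2.1, 13.7.2.1). One programmer could treat it as describing the 30% threshold and another as an extra filter.

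**Working it through.** The documents give no expected rate or power for this endpoint, so there is no planned figure to reproduce. The check compares the two rules.

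**1. How long must a fall last under the two-visit reading?** The gap is the nominal interval plus or minus the sum of the two visit windows (Schedule of Events).

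| Visit pair | Nominal (days) | Windows (days) | Range (days) |
|---|---|---|---|
| Weeks 2–4 | 14 | 3 + 3 | 8–20 |
| Weeks 4–8, 8–12, 12–16, 16–20 | 28 | 3 + 3 | 22–34 |
| Weeks 20–24 | 28 | 3 + 10 | 15–41 |
| Weeks 24–30, 30–36, 36–42, 42–48 | 42 | 10 + 10 | 22–62 |
| Weeks 48–52 | 28 | 10 + 10 | 8–48 |

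SAP 6.11.1 sets a minimum of 3 days. Week 52 has no later visit in the 6.11.4.2 list. The only later scheduled value is Week 56, which is not collected from subjects entering the continuation study.

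**2. Does a prompt retest count as a second time point?** Take Week w as day 7w + 1. A value from Week 4 is on day 29 and Week 8 is day 57, so the midpoint is day 43. A retest 3 to 7 days after Week 4 (days 32 to 36) maps to Week 4. It replaces the first value under that label and does not create a second time point.

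**3. Example courses.** Assume a baseline of 80, so a fall above 30% means eGFR below 0.70 × 80 = 56.

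| Course | 3-day rule, all values | 6.11.4.2 with 6.2.11 mapping |
|---|---|---|
| Week 4: 50; retest 3–7 days later: 52; Week 8: 74 | confirmed | not confirmed |
| Same, retest 1–2 days later | not confirmed | not confirmed |
| Week 2: 50; retest 8 days later: 51; Week 4: 75 | confirmed | not confirmed |
| Week 52: 50; retest 4 days later: 51; no Week 56 value | confirmed | not confirmed |
| Week 4: 50; Week 8: 52 | confirmed | confirmed |

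In the third row the retest (day 23) is nearer Week 4 than Week 2, but the later scheduled Week 4 value replaces it.

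**4. Can the effect be sized?** Let p be the proportion confirmed by the 3-day rule in an arm, and r the share of these that recover before the next visit. The two-visit rule counts p(1 − r), so the arm difference becomes p_V(1 − r_V) − p_P(1 − r_P). The documents give neither p nor r. Purely assumed values show how wide the answer is. Take p = 15% v 5%, a difference of 10 points:

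- r = 0 in both arms: 15% v 5%, difference 10 points.
- r = 50% in both: 7.5% v 2.5%, difference 5 points.
- r = 50% v 25%: 7.5% v 3.75%, difference 3.75 points.
- r = 75% v 25%: 3.75% v 3.75%, no difference.

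The result runs from no loss to complete loss, so no size is claimed.

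**The case against.** Several points on the other side stand.

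- **A sustained-fall rule is legitimate.** Protocol 5.6.1 itself uses a >30% fall in two successive measurements at least 4 weeks apart, close to the spacing of most visits. The 3-day rule was written for another endpoint and, in 6.11.2.3, a 20% threshold. This is inconsistent use of one word, not a contradiction within one endpoint.
- **Scheduled is an inference.** The sentence in 6.11.4.2 does not contain the word. If unscheduled draws were meant to count, the consequence disappears. SAP 6.2.13 (eGFR) is in the table of contents, but its text was not in the copy available for this review, so a definition there cannot be excluded.
- **The affected group is limited.** Interruption under Protocol 7.6.1.1 also requires eGFR below 60. That section's further retest within 48 hours would fail a 3-day minimum too.
- **Acute falls remain visible elsewhere:** eGFR and creatinine change by visit, adverse events including those leading to discontinuation, dose changes and listings. None of these, however, gives the proportion with a >30% fall confirmed on retest.

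Two stronger readings are tempting and are not supported. A reader might size the loss from Protocol 1.2.5, where decreased-GFR events "resulted in permanent discontinuation of study drug in 1 (1.1%) placebo subject, 6 (6.7%) voclosporin low-dose subjects". Those are permanent stops for an adverse event. They are not stated to be >30% falls, they carry no recovery fraction, and they are cumulative rates, whereas Table 14.2.7 reports proportions at each visit. A reader might also infer that bias in favour of voclosporin is established. Protocol 2.1 calls the risk reversible but gives no timescale. Protocol 1.2.5 says the proportion with an early drop stayed stable, and 1.2.4.2 says eGFR stabilised after Week 4.

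**Conclusion.** The two rules differ, and on the most natural reading the difference matters: a >30% fall that the trial confirms by retest and that recovers before the next scheduled visit is scored as no drop. This probably under-counts acute reversible falls, plausibly more on voclosporin. The direction is an inference from the drug class and Protocol 2.1, and the size cannot be derived from the documents.

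The conclusion assumes that time points means scheduled visits, that the 6.2.11 mapping applies to this table, and that SAP 6.2.13 does not say otherwise. The primary result and the control of type I error are untouched. What is at stake is the reading of a renal-safety endpoint, which justifies a correction but nothing larger.

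**What to change.** In SAP 6.11.4.2:

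1. State that scheduled and unscheduled central-laboratory eGFR values both count, so that the latest-value-per-visit convention in 6.2.11 does not remove a retest.
2. Report the proportion confirmed by the 6.11.1 rule: two successive values, 3 or more days apart, both more than 30% below baseline. Credit the fall to the visit of the first value, as the section already does.
3. Report the two-consecutive-visit version beside it, labelled sustained decrease.
4. Delete the undefined clinical-significance qualifier.
5. Note that retests less than 3 days apart still do not confirm under this rule.

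If 6.2.13 contains a confirmation rule, bring it into line with this one.

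The cost is SAP wording, one extra programmed flag and a somewhat less favourable reported rate. No new data are needed, provided the retests were analysed centrally; Protocol 9.1.1 bases all laboratory analyses on central results, so a retest run only locally would not count. No change to clinical management is proposed.

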  - 3 Subjects who do not enroll into the continuation study will have a follow up safety visit 4 weeks after the last dose of study treatment.
  - 4 If a subject has not had a recent kidney biopsy, one may be performed to assess eligibility for the study provided informed consent has been given and results are received prior to randomization. If one is performed as part of standard of care after randomization, the results will be recorded in the electronic case report form.
  - 5 Complete physical examination at screening, abbreviated examination at all other applicable visits. Height is measured at screening only.
  - 6 During the study, and after screening, in the event that a subject is noted to have a QTcF value exceeding 500 msec, or >60 msec more than baseline, the ECG will be repeated; see Section 9.1.4.1, [Procedures to Manage a Treatment-Emergent Increase in QTc](#). Electrocardiograms will be recorded digitally after the subject has been in a resting, supine position for at least 5 minutes.
  - 7 Week 12 only.
  - 8 Laboratory assessments will be performed according to the schedule in Section 9.1.1, [Laboratory Assessments](#); subjects must be fasting for at least 8 to 12 hours at baseline and end of study/early termination.
  - 9 Blood samples will be collected at 0 and 2 hours post dose for pharmacokinetics.
  - 10 Two FMV specimens, to be performed and resulted before baseline.
  - 11 24-hour urine collection should begin 2 days prior to the scheduled study visit in order not to coincide with the FMV sampling due on the day of the study visit.
  - 12 Serum pregnancy test to be evaluated at central laboratory at screening, Week 24, and Week 52; urine pregnancy test will be performed locally at all other applicable visits.
  - 13 Adverse events will be recorded after the subject signs the ICF; AEs which occur during screening or prior to the first dose of study treatment will not be considered TEAEs.
  - 14 Concomitant medications include all herbal medicines and supplements taken by the subject.
  - 15 For details on HRQoL assessments, see Section 9.3.1, [Health-related Quality of Life Assessments \(HRQoL\)](#).
  - 16 For details on Healthcare Resource Utilization, see Section 9.3.2, [Healthcare Resource Utilization Assessment](#).
  - 17 Compliance only.
  - 18 All scheduled procedures must be done prior to first dose, including IV methylprednisolone and MMF.

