## 4. INVESTIGATIONAL PLAN

### 4.1 Overall Study Design

This is a Phase 3, multicenter, randomized, prospective, double-blind, parallel-group, placebo-controlled, 2-arm comparison study of Orelvo versus matching placebo. Subjects who have provided a signed and dated informed consent will be screened into the study up to 30 days before randomization. During the screening period, eligibility criteria will be assessed. A kidney biopsy may be performed, provided the subject has given consent and provided the results can be obtained and reviewed before baseline. Subjects who meet all of the inclusion criteria and none of the exclusion criteria will be eligible for randomization into the study.

Baseline assessments will be performed before the first dose of study treatment is administered on Day 1. The baseline assessments of the serum creatinine and urine protein laboratory parameters will be established by using the mean of the 2 pre-randomization values. Using an interactive web response system (IWRS), eligible subjects will be randomized to receive either oral Orelvo 23.7 mg BID or matching placebo for 52 weeks. All subjects should receive 0.5 g/day IV methylprednisolone on Days 1 and 2 before changing to a reducing course of oral corticosteroid therapy on Day 3. (For additional details and exceptions, see Section 7.2.2.2, [Corticosteroids](#)). Starting at the Baseline Visit, all subjects will also receive background therapy with MMF (see Section 7.2.2.3, [Mycophenolate Mofetil \(Background Therapy\)](#)).

All subjects will return for assessment of efficacy and safety at Day 2 and Weeks 2, 4, 8, 12, 16, 20, 24, 30, 36, 42, 48, and 52. See [Schedule of Events](#), for detailed information regarding visits. In addition, subjects not on MMF during screening, will start receiving MMF at the Baseline Visit and will return for local complete blood count assessments at Weeks 1 and 3 after randomization.

All subjects, completed or withdrawn, will complete the End of Treatment/Early Termination assessments (Visit 15) at Week 52 or at the time of early termination. Subjects who do not enroll in the continuation study will attend the Safety Follow-up Visit (Visit 16) at Week 56 to collect any new AEs and concomitant medications. At the follow-up visit, UPCR and eGFR will be assessed as well. For subject withdrawal procedures and criteria, see Section 5.5, [Withdrawal of Subjects](#).

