## **5.6 Discontinuation of Study Treatment**

If any subject is discontinued from study treatment, the reason for discontinuation will be documented in the eCRF. If the reason for discontinuing study treatment is an AE or an abnormal laboratory test result, the specific event or test will be recorded in the eCRF. Except for cases involving pregnancy, subjects who are discontinued from study treatment should undergo all study assessments up to and including (Week 52 or Early Termination Visit – Visit 15), if possible. The subject should also be advised to come for the Safety Follow-up Visit 4 weeks after last dose. Guidance on when study treatment must be discontinued is in Section 7.6, [Orelvo/Placebo Dose Modification](#).

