### **9.2.4 Follow-up Procedures**

All subjects who complete the study but do not participate in the continuation study or discontinue study treatment before Week 52 will be followed up 4 weeks ( $\pm 10$  days) after their last study treatment dose to collect any new AEs and concomitant medications. This visit (Visit 16) will be conducted as an in-clinic visit.

Assessments for the follow-up visit are as follows:

- Vital signs
- Blood sample collection for analysis at central laboratory (eGFR)
- First morning void urine sample collection
- Concomitant medication
- AEs
- Confirmation of completed follow-up visit using IWRS

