### **6.2.3 Early Terminations Assessments**

Data collected at Early Termination (ET) assessments will be mapped to the visits closest to the date of termination.

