### **6.2.12 Randomization Strata**

The randomization will be stratified by biopsy class (Class V only versus Others) and by prior MMF use at time of screening. A regional blocking factor will also be used for supply purposes ensuring balance within region. The stratification factors and the regional blocking factor will be used as covariates in the primary analyses.

Tables of events or medications will be ordered in descending frequency of subjects followed by (where applicable) events for the higher level term (system organ class or ATC levels 4 and 2) followed by the preferred term. Ordering will be for the VCS treatment group first followed by the placebo group and alphabetical thereafter.

Listings will be sorted in the following order treatment group, subject, parameter, and visit unless otherwise stated. All data will be listed, subjects who were not randomized will be displayed after the randomized treatment groups.

Continuous variables will be summarized by the number of non-missing observations, mean, median, standard deviation, and minimum and maximum. For all tabulations of changes from baseline data, the lower and upper 95% confidence limits for the mean for the individual treatments will be given.

Categorical variables will be summarized by presenting the frequency and percent. Percentages will be based on the number of non-missing observations out of the subject population unless otherwise specified. For each variable, all categories will be shown. Zero frequencies (but not the percent) within a category will be presented.

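### SAP 6.11.4.2 credits a confirmed >30% eGFR decrease only at the earlier of two time points, so its Week 52 row is either empty or rests on later values the available text does not say may be used

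*SAP*

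**What the plan says.** SAP 6.11.4.2 looks for a decrease of more than 30% from baseline at any two consecutive time points. A subject who meets this "will be considered a confirmed eGFR drop subject at the earlier timepoint, otherwise they will be considered a non-eGFR drop subject".

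The same section fixes the rows of the table: "The proportion of eGFR drop subjects will be summarized at weeks 2, 4, 8, 12, 16, 20, 24, 30, 36, 42, 48 and 52". The arms are compared by chi-square or Fisher's exact test, and a p-value is reported at each visit (Table 14.2.7).

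The only scheduled visit after Week 52 is Visit 16. Protocol 4.1 states: "Subjects who do not enroll in the continuation study will attend the Safety Follow-up Visit (Visit 16) at Week 56". Footnote 3 of the protocol's Schedule of Events gives the timing from the last dose: "Subjects who do not enroll into the continuation study will have a follow up safety visit 4 weeks after the last dose of study treatment". Protocol 9.2.4 repeats that timing with a window of ±10 days and includes an eGFR sample at the visit.

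Two protocol sections call for extra eGFR values. Section 9.2.5 requests an unscheduled visit for a fall of more than 30%. Section 7.6.1.1 requires a repeat test during treatment when such a fall takes eGFR below 60. SAP 6.2.11 maps every visit, scheduled or not, to the closest scheduled one and tabulates the latest value in by-visit summaries.

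For the primary endpoint, SAP 6.11.1 and 6.11.2.3 define confirmation differently: two consecutive measurements at least 3 days apart, complete by the visit at which response is judged.

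**The concern.** The rule looks forward only, and the last row of the table has no listed visit to look forward to. Week 52 is the end-of-treatment row of a renal endpoint named in the protocol, for a calcineurin inhibitor. A reader going down Table 14.2.7 would expect the Week 52 row to show how many subjects had a confirmed fall at the end of treatment. As written, a sustained difference between the arms could shrink or vanish between Weeks 48 and 52 because of the crediting rule and not because renal function recovered. The Week 52 p-value would carry the same artefact.

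**Working it through.** **Inputs.** The rule, the 12 visits and the tests come from SAP 6.11.4.2. Visit 16 timing comes from Protocol 4.1, 5.6, 9.2.4 and the Schedule of Events. The planned 162 per arm (SAP 4) serves only as an illustrative denominator. The plan states no numerical figure for this endpoint, so there is none to reproduce.

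**Step 1: pairs.** Weeks 2, 4, 8, 12, 16, 20, 24, 30, 36, 42, 48 and 52 give 12 − 1 = 11 consecutive pairs. Their earlier members are Weeks 2 to 48. Week 52 is the earlier member of 0 of 11.

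**Step 2: the rule applied to example courses.**

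| Visits more than 30% below baseline | Later value | Rows credited |
|---|---|---|
| Weeks 48, 52 | none | 48 |
| Weeks 36, 42, 48, 52 | none | 36, 42, 48 |
| Weeks 48, 52 | Visit 16 also low, and allowed to count | 48, 52 |

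**Step 3: only the listed visits count.** The Week 52 row is 0/162 v 0/162 by construction. Fisher's test gives p = 1. The expected event counts are zero, so chi-square is undefined. As an illustration with assumed counts, let falls persist through Weeks 48 and 52 in 32/162 (19.8%) v 8/162 (4.9%). Week 48 then shows Fisher p = 0.00007 and Week 52 shows p = 1, from the same subjects with the same eGFR values.

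**Step 4: Visit 16 counts.** For completers it falls 28 ± 10 = 18 to 38 days after the last dose, so the confirming value is off drug. Let c be the share of subjects with a Week 52 fall who have no later value, and s the share of the rest who are still more than 30% below baseline at Visit 16. If repeats do not count:

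share of Week 52 falls that register = (1 − c) × s

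- c = 0, s = 1: 100%
- c = 0.5, s = 0.5: 0.5 × 0.5 = 25%
- c = 1 or s = 0: 0%

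The documents give neither c nor s, so the range is 0 to 100%. At 25%, the assumed 32 v 8 would appear as 8 v 2 (Fisher p = 0.10).

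The share with a later value need not be equal in the two arms. Take an assumed true rate of 10% in both arms, with every fall persisting. Later values for 20% v 40% of subjects would show 0.10 × 0.20 = 2% v 0.10 × 0.40 = 4%. Reversing the shares reverses the difference.

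**Step 5: unscheduled repeats.** Under SAP 6.2.11 a repeat soon after Week 52 maps to Week 52 and, as the latest value, becomes the tabulated one. On that wording it replaces the Week 52 value and does not form a second time point. The SAP does not say whether the mapping also governs confirmation.

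**Step 6: can Week 48 confirm Week 52?** The visits are nominally 28 days apart, each with a ±10-day window. The shortest in-window gap is 28 − 20 = 8 days, which exceeds the 3-day minimum in SAP 6.11.1 and 6.11.2.3. The pair therefore meets the interval the SAP already uses elsewhere.

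**The case against.** The best reply is that the empty row is only one reading. SAP 6.11.4.2 speaks of any two consecutive time points; it lists the weeks to be summarized and does not limit confirming values to them. Visit 16 is scheduled and has an eGFR sample, and the protocol calls for repeats after a fall of this size. The SAP's contents also list a section 6.2.13 on eGFR that is absent from the copy available here and may settle what counts. All of this stands. It rules out saying that the row must be empty. It does not rescue the row, because a value from Visit 16 is missing for subjects in the continuation study and off drug for completers, and no available text says that repeats confirm.

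A reader might infer that subjects who stop drug early never have a value after Week 52, since Protocol 5.6 says: "The subject should also be advised to come for the Safety Follow-up Visit 4 weeks after last dose". The documents do not settle this. Protocol 4.1 and the Schedule of Events place Visit 16 at Week 56, while 5.6 and 9.2.4 time it from the last dose.

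A reader might also infer that scoring a fall with no later value as no drop is an error at every visit. Percentages use non-missing observations (SAP text following 6.2.12), so such a subject does stay in the denominator. But an isolated last fall is unconfirmed by the meaning of the term, and subjects who stop drug are expected to keep attending. This is largely inherent in a confirmed endpoint. Requiring persistence to the next visit at earlier weeks is likewise a defensible choice.

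The reply that little depends on the row is fair. A Week 48 and 52 fall still appears at Week 48, and eGFR change at Week 52, the Week 52 eGFR components of response and the adverse event tables all remain.

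**Conclusion.** The point holds for the Week 52 row. A stated rule, applied as written, gives a proportion and p-value that cannot be read as a comparison of confirmed falls at Week 52. The row is 0% v 0% if only listed visits count. If Visit 16 counts and repeats do not, it captures an unknown 0 to 100% of Week 52 falls. Whether repeats count is a matter for clarification, not a demonstrated error, given the missing SAP 6.2.13.

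The harm is limited to Table 14.2.7, which SAP 9 places outside the key secondary endpoints and so outside the Hochberg procedure. The primary endpoint has its own confirmation rule and is untouched. A reader might infer that the rule hides a renal signal or favours one arm. The documents support neither, because the size and direction of any bias between arms cannot be derived from them. The 32/162 v 8/162 counts, the values of c and s, and the unequal follow-up shares are assumptions chosen to show the mechanism.

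**What to change.** In SAP 6.11.4.2:

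1. Let a Week 52 fall be confirmed by the Week 48 value, or by a repeat at least 3 days apart, in line with SAP 6.11.1 and 6.11.2.3.
2. Footnote Table 14.2.7 to say that Week 52 looks backward while earlier rows look forward, so one Week 48 and 52 pair can count in both rows.
3. State whether Visit 16 and unscheduled repeats count as time points, and how this fits the mapping in SAP 6.2.11. If Visit 16 counts, reconcile its two timings for subjects who stopped drug early.
4. Optionally, show beside each row the number of falls with no later value, by arm.

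The cost is a few sentences of SAP text and the reprogramming of one table on data already collected. Reported Week 52 rates may rise. A fall first seen at Week 52 still needs a repeat, or Visit 16 if that is allowed. Looking backward at every visit would give a single rule but would move the empty row to Week 2 unless repeats count. The protocol's clinical-management rules need no change for this.
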